# **PROJECTION OF VISUAL MATERIAL ON POSTOPERATIVE DELIRIUM IN PATIENTS UNDERGOING CARDIAC SURGERY: A DOUBLE BLIND RANDOMIZED CLINICAL TRIAL**

The general objective of this study is to evaluate the impact of visual projection of images of relatives or loved ones in patients undergoing cardiac surgery in the immediate postoperative period, and its influence on the incidence and development of postoperative delirium.

## **METHODOLOGY**

### **Design**

A double-blind randomized clinical trial (RCT) with an intervention group (IG) and a control group (CG). The study is carried out among patients undergoing cardiac surgery at León University Assistance Complex between July 2021 and January 2022.

The control group received the usual treatment from the unit for postoperative delirium, based mainly on the use of haloperidol and/or dexmedetomidine, as well as mechanical restraints when the patient required it, while the intervention group received a visual projection of images of relatives or loved ones as a method of prevention and treatment of postoperative delirium.

The study followed the Consolidated Statement of Reporting Trials (CONSORT) guidelines. The protocol complied with the Declaration of Helsinki and has been approved by the Drug Research Ethics Committee (CEIm) of León University Assistance Complex with number/reference 2155.

### **Population**

The study population consisted of patients undergoing heart surgery (aortic valve replacement, mitral valve replacement and/or coronary bypass) in the immediate postoperative period during their stay in the cardiac resuscitation unit. All patients included in the study are over 18 years of age. The patients decided to participate voluntarily, after having been informed of the purpose of the study, as well as what their participation consisted of, by signing an informed consent.

### **Sample**

The estimated sample size for a difference between two proportions, with a statistical power of 80% for an alpha significance level of 0.05 with a prevalence of postoperative delirium of 30% and a rate of loss to follow-up of 10%, is 52 patients per group.

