### **Development of the intervention**

Patients are randomized into two groups (control group and intervention group) after explaining the study and offering voluntary participation.

Initially, regardless of the group to which they belonged, all patients are administered the MMSE scale to assess their initial cognitive state and their sociodemographic and anthropometric data are collected.

In the intervention group, patients and/or companions are asked to provide visual material, which could consist of photographs of loved ones and/or places known to the patient. Once the surgical intervention is completed, the patients are transferred to the Cardiac Resuscitation Unit. 30 minutes after the extubation of the patients, the CAM-ICU scale is administered, recording its value as R0. Next, the projection of images provided by the patient began until 11:30 p.m., at which time these images are replaced by a nocturnal visual projection (night sky with stars and moon), ensuring that the patient is able to identify that it is nighttime. Later, at 7:00 p.m. the visual projection is removed and the record sheet is completed with the anesthetic and surgical data. Finally, at 9:00 a.m., a nurse who had not worked at night and therefore did not know which patients had received the intervention, administered the CAM-ICU scale again, recording its value as R1.

In the control group, we proceeded as follows: after the surgical intervention and after the patient is admitted to the Unit, we waited 30 minutes after the patient's extubation to administer the CAM-ICU scale, recording its value as R0. The following day, at 7:00 a.m., the record sheet is completed with the anesthetic and surgical data, and finally, at 9:00 a.m., another nurse administered the CAM-ICU scale, noting its value as R1, without knowing which patients belonged to each group. If postoperative delirium is detected during the day and night, the unit's usual treatment is followed: administration of haloperidol and/or dexmedetomidine if the patient showed agitation.

Finally, a member of the research team, who did not know which patients had received the intervention, analyzed the data obtained without knowing what each variable referred to.

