## **Statistical analysis**

The information is recorded in a database created with the Excel computer program. Statistical analysis is performed with Epi Info™ 7.2 software and R Studio version 1.3.1093.

For the descriptive analysis of the variables, the mean, standard deviation, minimum, and maximum values are calculated for the quantitative variables, and the relative frequencies and percentages are calculated for the qualitative variables.

For the study of the association between categorical variables, the chi-square statistic or Fisher's exact test is used when the data are independent, while for the related data the McNemar test is used for two groups, transforming the variables into dichotomous ones for its analysis. Stratified analysis is performed using the Mantel-Haenzsel test.

For the multivariate analysis, the logistic regression model is used, including the variables included in the analysis. The stepAIC function from the R MASS package is used.

To validate the results, in terms of significance, a confidence level of 95% is used and any value of  $p < 0.05$  is considered significant.

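### The 80% power holds only for a fall in delirium from 30% to about 6–9%, which is not stated, and the analysis specifies no effect estimate or interval and does not protect the group term

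*SAP*

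**What the plan says.** The Sample section describes a calculation for a difference between two proportions, with "a statistical power of 80% for an alpha significance level of 0.05", and continues "with a prevalence of postoperative delirium of 30% and a rate of loss to follow-up of 10%, is 52 patients per group". It gives no rate for the second group and no difference. It does not say which arm the 30% describes, whether the test is one- or two-sided, or whether a continuity correction was used.

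For the group comparison, the Statistical analysis section says "the chi-square statistic or Fisher's exact test is used when the data are independent". It does not say when each test applies or whether the chi-square is corrected. A Mantel-Haenszel stratified analysis is planned without a named stratum. Logistic regression follows, with "The stepAIC function from the R MASS package is used". The criterion for a conclusion is that "in terms of significance, a confidence level of 95% is used and any value of" p below 0.05 counts as significant. The 95% there is a significance level. No risk difference, risk ratio or odds ratio is named as the treatment effect, and no confidence interval is planned for one.

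Development of the intervention records CAM-ICU as R0 in both arms 30 minutes after extubation. In the intervention arm, "Next, the projection of images provided by the patient began until 11:30 p.m" follows that reading. R1 is taken at 9:00 a.m.

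**The concern.** Power is a statement about a particular effect, so a claim of 80% with no effect attached cannot be interpreted. The fixed sample size does allow the implied effect to be recovered, and it is very large. If the true benefit is smaller but still worthwhile, the likely result is p above 0.05 from a trial described as having 80% power. With only a significance criterion in the plan, that result is easily read as evidence that the projection does not work.

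The logistic model could supply an estimate, but stepwise AIC selection is free to remove the group variable. It does so when the group effect is weak in the data, which is when an estimate with its interval is most needed.

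**Working it through.** **Inputs.** From the Sample section: alpha 0.05, power 80%, one proportion 30%, loss 10%, 52 per group. Assumptions: 30% is the usual-care rate; the test is two-sided; evaluable patients per group are 47 (52 × 0.9 = 46.8) if the loss is already in the 52, or 52 if not.

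**1. Can 52 be reproduced?** Not forwards, because the second proportion is missing. Trying 6%, with mean proportion 0.18:

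- Without correction: n = [1.960 × √(2 × 0.18 × 0.82) + 0.842 × √(0.30 × 0.70 + 0.06 × 0.94)]² / 0.24² = 39.0.
- With continuity correction: n = (39.0/4) × [1 + √(1 + 4/(39.0 × 0.24))]² = 47.0.
- With loss: 47.0/0.9 = 52.2, or 47.0 × 1.1 = 51.7.

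So 52 is consistent with 30% versus 6%. This is one route to the number; the SAP does not say that it was the one used.

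**2. Which effect has 80% power?** Full enumeration of the binomial tables gives the highest intervention rate with at least 80% power against 30%:

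| Evaluable per group | Chi-square, uncorrected | Chi-square, corrected | Fisher |
|---|---|---|---|
| 47 | 8.2% | 6.4% | 6.4% |
| 52 | 8.9% | 7.3% | 7.6% |

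The range is 6.4% to 8.9%, a relative fall between (30 − 8.9)/30 = 70% and (30 − 6.4)/30 = 79%.

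**3. Power for a halving, 30% versus 15%**, by the same enumeration:

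| Evaluable per group | Chi-square, uncorrected | Chi-square, corrected | Fisher |
|---|---|---|---|
| 47 | 42% | 32% | 32% |
| 52 | 46% | 35% | 37% |

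**4. What an observed halving gives:**

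| Observed | Chi-square p, uncorrected | Fisher p | Fall, with Newcombe 95% interval |
|---|---|---|---|
| 14/47 vs 7/47 | 0.083 | 0.136 | 14.9 points (−2.1 to 30.9) |
| 16/52 vs 8/52 | 0.063 | 0.102 | 15.4 points (−0.9 to 30.8) |

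Both intervals include no effect. Both also include falls larger than the 21 to 24 points for which the trial has 80% power. The p-value alone does not show this.

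**5. Does the choice of test matter?** Near the boundary, yes. For 14/47 versus 6/47, p is 0.044 by uncorrected chi-square, 0.078 by corrected chi-square and 0.076 by Fisher. The SAP leaves open which applies.

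**6. What stepAIC can do to the group term.** AIC charges 2 per parameter. A one-parameter group term is therefore removed when dropping it lowers the likelihood-ratio chi-square by less than 2. Nothing in the Statistical analysis section exempts it. How often this would happen depends on the other variables in the model, which the SAP does not list, so no frequency is given here.

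**7. Other readings of the inputs.**

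- One-sided uncorrected chi-square: 80% power needs a fall to 10.2–10.9%.
- 30% as the average of both arms: the gap needed is 25–28 points.
- 30% as the intervention rate: the gap is about 26.5–31 points, and the halving figures do not apply.

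None of these readings brings the required gap below about 19 points (30 − 10.9 = 19.1).

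**The case against.** The strongest reply is that nothing is miscalculated. Step 1 shows that 52 can be recovered, and at 30% versus 6% with 47 per group the exact power is 90% by uncorrected chi-square and 83% by Fisher. The justification for so large an effect may be in a protocol that is not at hand, and the SAP nowhere makes a halving its target. All of that stands. The halving is this review's benchmark, not the trial's, and no claim is made that a 70–79% reduction is impossible. What remains is that the SAP states a power without the effect that defines it.

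A reader might infer that any observed halving must miss p < 0.05. That is not so: 18/52 versus 9/52 gives p = 0.044 by uncorrected chi-square, and 20/47 versus 10/47 gives 0.046 by Fisher. The result in step 4 applies when the observed control rate is close to 30%.

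A reader might also infer that the plan can produce no effect size outside the logistic model. It can: the Mantel-Haenszel analysis can give a common odds ratio, and the planned percentages allow a risk difference to be worked out. The gap is that no measure is specified as the result and no interval is planned.

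Finally, because R0 precedes the projection, a reader might infer that delirium already present caps the achievable effect. The SAP gives no R0 rate. It also describes the projection "as a method of prevention and treatment of postoperative delirium", so resolving existing cases is part of its aim. That inference is not supported.

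**Conclusion.** The concern holds as an interpretation and analysis problem, not as an error in the number 52. On the assumptions of a 30% usual-care rate and a two-sided 0.05 test, the stated 80% power belongs to a fall to about 6–9%. For a halving, power is 32–46%. The limits depend on the test and on whether 47 or 52 per group are evaluable. The alternative readings change the figures but not the conclusion that only a very large effect is covered.

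The missing second proportion would, by itself, be a missing detail. It matters because the analysis section relies on p < 0.05, specifies no effect measure or interval, leaves the test open and lets stepwise selection remove the treatment term. As written, the plan does not ensure that an inconclusive result can be told from a negative one. It should be corrected.

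**What to change.** **Statistical analysis section:**

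- Make the between-group risk difference in CAM-ICU positivity at R1, with its 95% confidence interval, the main result. Newcombe's interval is one suitable choice.
- Report beside it one test under a rule fixed in advance. An example is two-sided chi-square without continuity correction, with Fisher only if an expected count is below 5.
- Force the group term into the logistic model, so that stepAIC selects among the other variables only.
- Use R0 as a stratum in the planned Mantel-Haenszel analysis. It is recorded before projection starts, and stratifying shows new and persisting delirium separately. This suits an objective that covers "its influence on the incidence and development of postoperative delirium".
- State that p ≥ 0.05 will be reported with the interval and not as absence of effect.

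**Sample section:** restate the 80% as holding for about 30% versus 6–9%, and name the arm to which the 30% refers and the sidedness of the test.

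**Cost:** a few sentences. Group, R0 and R1 are already collected, so no new data or patients are needed. The price is a stated power that looks less favourable.

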### **Randomization and blinding of the sample**

A control group is established, on which the usual practice of the unit regarding postoperative delirium is carried out, as well as an intervention group on which visual material is projected in the resuscitation box. Randomization of participants into one or the other group is ensured using OxMaR computer software.

The masking of the sample is double blind. Neither the observer who administered the measurement scale nor the investigator who analyzed the data knew whether the subjects had received the study intervention or not.

### **Inclusion and exclusion criteria**

The inclusion criteria involved: undergoing elective cardiac surgery, the requirement of admission to the cardiac resuscitation unit, being over 18 years of age, agreeing to participate in the study, not being sedated for at least 24 hours, presenting an adequate level of consciousness and being able to communicate in Spanish. All patients who did not meet any of the inclusion criteria are excluded, as well as those who underwent emergency surgery or those who did not require admission to the cardiac surgical resuscitation unit.

### **Variables**

These consisted of sociodemographic variables such as age and gender, anthropometric weight, height, BMI. Social variables consisted of whether the patient lived alone or accompanied etc., as well as surgical, anesthetic and postoperative care characteristics such as the type of intervention, use of drugs, time mechanical ventilation or extracorporeal circulation, etc.

Variables related to postoperative delirium are also collected, such as the positive or negative result of the CAM-ICU scale, as well as those related to the projection of visual material, pharmacological measures or mechanical restraints used.

Finally, the objective score obtained in the Mini-mental State Examination (MMSE) is recorded in order to assess the patient's prior cognitive status.

### **Instrument**

An "ad hoc" registration sheet is prepared in order to facilitate data collection. The record sheet contained sociodemographic data, surgical and anesthetic characteristics, as well as postoperative and postoperative delirium care. In addition, the CAM-ICU scale as well as the Mini-Mental State Examination is applied to the patients included in the study. The CAM-ICU scale is a validated scale and it is the most frequently used scale to assess the presence of delirium in critical care units, while the Mini-Mental State Examination scale is used to assess the patient's previous cognitive state.

The estimated time for completing the record sheet is 4 minutes and 7 minutes for the administration of each of the both scales. Confidentiality is ensured at all times through alphanumeric coding so as to avoid the recording of their personal data.

### **Development of the intervention**

Patients are randomized into two groups (control group and intervention group) after explaining the study and offering voluntary participation.

Initially, regardless of the group to which they belonged, all patients are administered the MMSE scale to assess their initial cognitive state and their sociodemographic and anthropometric data are collected.

In the intervention group, patients and/or companions are asked to provide visual material, which could consist of photographs of loved ones and/or places known to the patient. Once the surgical intervention is completed, the patients are transferred to the Cardiac Resuscitation Unit. 30 minutes after the extubation of the patients, the CAM-ICU scale is administered, recording its value as R0. Next, the projection of images provided by the patient began until 11:30 p.m., at which time these images are replaced by a nocturnal visual projection (night sky with stars and moon), ensuring that the patient is able to identify that it is nighttime. Later, at 7:00 p.m. the visual projection is removed and the record sheet is completed with the anesthetic and surgical data. Finally, at 9:00 a.m., a nurse who had not worked at night and therefore did not know which patients had received the intervention, administered the CAM-ICU scale again, recording its value as R1.

In the control group, we proceeded as follows: after the surgical intervention and after the patient is admitted to the Unit, we waited 30 minutes after the patient's extubation to administer the CAM-ICU scale, recording its value as R0. The following day, at 7:00 a.m., the record sheet is completed with the anesthetic and surgical data, and finally, at 9:00 a.m., another nurse administered the CAM-ICU scale, noting its value as R1, without knowing which patients belonged to each group. If postoperative delirium is detected during the day and night, the unit's usual treatment is followed: administration of haloperidol and/or dexmedetomidine if the patient showed agitation.

Finally, a member of the research team, who did not know which patients had received the intervention, analyzed the data obtained without knowing what each variable referred to.

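### The R1 rater's blindness rests on not having worked at night, but the family images are on display before the night begins

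*SAP*

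**What the plan says.** The schedule for the intervention arm is in the SAP, Development of the intervention:

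- Baseline reading: "30 minutes after the extubation of the patients, the CAM-ICU scale is administered, recording its value as R0".
- Family images: "Next, the projection of images provided by the patient began until 11:30 p.m".
- From 11:30 p.m. these are "replaced by a nocturnal visual projection (night sky with stars and moon), ensuring that the patient is able to identify that it is nighttime".
- Removal: "Later, at 7:00 p.m. the visual projection is removed and the record sheet is completed with the anesthetic and surgical data".
- R1 at 9:00 a.m., rated by "a nurse who had not worked at night and therefore did not know which patients had received the intervention".

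In the control arm the corresponding paperwork step is "The following day, at 7:00 a.m., the record sheet is completed with the anesthetic and surgical data". R1 is then taken by another nurse, who is said not to know the groups; no reason is given for that.

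Under Randomization and blinding of the sample, the SAP describes "an intervention group on which visual material is projected in the resuscitation box" and states the blinding in general terms: "Neither the observer who administered the measurement scale nor the investigator who analyzed the data knew whether the subjects had received the study intervention".

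**The concern.** The word "therefore" would be justified only if the intervention could be seen at night and at no other time. The same paragraph describes a phase before the night, and it is the more revealing one, because it shows the patient's own photographs in the box.

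CAM-ICU is rated by an observer, and R1 is the only reading scheduled after the projection starts. The patients see the images, so the double-blind label depends on the rater and the analyst. Blinding the analyst cannot undo a rating already made with knowledge of the arm. If some raters knew which patients had the projection, intervention-arm scores could drift in the expected direction, and the plan gives no means of detecting it.

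**Working it through.** **1. Compare the two time windows.**

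| | Start | End |
|---|---|---|
| Family images visible in the box | just after R0 (30 minutes after extubation) | 11:30 p.m. |
| Night-sky projection visible | 11:30 p.m. | removal next morning |
| Duty that rules a nurse out as R1 rater | start of night work | end of night work |

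The hours from R0 to the start of night work are therefore not covered. A nurse present in those hours, off overnight and back at 9:00 a.m. is eligible under the stated rule.

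The printed removal time of 7:00 p.m. is a slip for 7:00 a.m.: it comes after the 11:30 p.m. step and before the 9:00 a.m. rating, and it matches the control-arm step. It carries no weight here.

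**2. How long is the gap?** The SAP gives neither extubation times nor shift hours, so this is illustration only. Projection starts at extubation + 30 minutes + about 7 minutes for the scale (Instrument section).

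- Extubation assumed at 3:00 p.m.: projection from 3:37 p.m. If night work starts between 8:00 and 10:00 p.m., the gap is 4 h 23 min to 6 h 23 min.
- Extubation assumed at 8:00 p.m.: projection from 8:37 p.m. The gap is zero to 1 h 23 min.

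The gap can be most of an afternoon and evening, or nothing.

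**3. What could it do to the test?** Inputs from the Sample and Statistical analysis sections: 52 per group, 10% loss, 30% delirium, significance at 0.05, chi-square test. Analysed per arm: 52 × 0.90 = 46.8, taken as 47.

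Assumptions that are not in the SAP: true delirium is 30% in both arms; a share *u* of intervention-arm ratings is unblinded; among those, a share *m* of true positives is scored negative; control ratings are unaffected. Then

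observed intervention rate = 0.30 × (1 − *u* × *m*).

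For example, *u* = 0.50 and *m* = 0.50 give 0.30 × 0.75 = 22.5%. The rejection probability of the two-sided chi-square test was obtained by exact enumeration of two binomials with 47 per arm and 30% in controls.

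| *u* | *m* | Observed intervention rate | Uncorrected | Continuity-corrected |
|---|---|---|---|---|
| none | – | 30.0% | 5.1% | 2.9% |
| 10% | 10% | 29.7% | 5.1% | 2.9% |
| 10% | 50% | 28.5% | 5.4% | 3.1% |
| 25% | 10% | 29.25% | 5.2% | 2.9% |
| 25% | 50% | 26.25% | 7.0% | 4.2% |
| 50% | 10% | 28.5% | 5.4% | 3.1% |
| 50% | 50% | 22.5% | 13.0% | 8.7% |

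The bias runs one way, so the two-sided rate understates its effect on false claims of benefit. Uncorrected, the probability of a false result favouring the intervention is 2.6% without bias, 6.0% with *u* = 25% and *m* = 50%, and 12.8% with both at 50%.

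**The case against.** **The facts that decide exposure are not shown.** The gap matters only if projection is visible before night work starts and a nurse present then also rates R1 next morning. With late extubations, or a roster that never follows an afternoon or evening shift with a morning one, it closes. This stands: no unblinding is shown. The stated reason still does not deliver what it claims.

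**Blinding is also stated outright.** The general statement and the control-arm sentence both say the rater did not know, so the night-work clause might be only an explanatory remark. But it is the only mechanism the SAP offers, and the other two statements assert the result without saying how it was achieved.

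**Rostering belongs in the protocol.** Silence on the point would be no fault in an SAP. Here the SAP is not silent: it gives a rule and draws a conclusion that does not follow.

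**The magnitude is assumed, and mostly small.** This stands. Apart from the extreme corner, every corrected rate stays below 5%, and 13.0% needs half the intervention-arm ratings unblinded and half of the true positives among them misscored.

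**The remedy is partial and may come late.** An awake patient may mention the pictures during the assessment, and a rostering rule does not prevent that. The study is dated July 2021 to January 2022, so the ratings may already be complete. Both points limit what the change achieves; neither is a reason to leave this route open or unreported.

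**Conclusion.** The point holds. By the SAP's own schedule, absence from night work does not imply ignorance of allocation, and nothing else in the document closes the gap. It is a weakness in the stated rule, with actual exposure unknown because extubation times and shift hours are not given.

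The size of any bias cannot be derived from the document. Across the assumed ranges the false-positive rate goes from no visible change to 13.0% uncorrected (8.7% corrected). The case for acting is that the change costs little and protects the only scheduled outcome reading after projection starts. It should be made; the trial does not stand or fall on it. Confidence is medium.

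**What to change.** Replace the night-work criterion with one tied to the projection itself, in both arms: the nurse who rates R1 must not have been on duty in the unit at any time from that patient's R0 until the projection is removed, or, for controls, until the 7:00 a.m. record-sheet step. Log any exception as a deviation. Correct the removal time to 7:00 a.m.

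If the ratings are already done, check the same rule against whatever duty rosters were kept and report the exceptions.

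The cost is one line of procedure and a rostering rule among existing nurses; no extra visits or patients are needed. On some mornings no eligible nurse may be on shift. How often cannot be judged without a roster. Such patients are rated anyway and logged as deviations.
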